#### **6.1.3 Reporting Requirements**

By participating in this study, the investigator agrees to submit reports of SAEs according to the time line and method outlined in the protocol (Section 4.7.3.1.2). In addition, the investigator agrees to submit reports to the IRB as appropriate. The investigator also agrees to provide the sponsor with an adequate report shortly after completion of the investigator's participation in the study.

### **6.1.4 Source Documentation**

By participating in this study, the investigator agrees to maintain adequate case histories for the subjects treated as part of the research under this protocol. The investigator agrees to maintain accurate eCRFs and source documentation as part of the case histories.

### **6.1.5 Retention of Records**

The investigator agrees to keep the records stipulated in this protocol and those documents that include (but are not limited to) the study-specific documents, identification log of all participating subjects, medical records, source worksheets, all original signed and dated informed consent forms, subject authorization forms regarding the use of personal health information (if separate from the informed consent form), copies of all eCRFs, query responses, and detailed records of drug disposition, to enable evaluations or audits from regulatory authorities, the sponsor, or its designees.

Furthermore, ICH 4.9.5 requires the investigator to retain essential documents specified in ICH E6(R1) (Section 8) until at least 2 years after the last approval of a marketing application for a specified drug indication being investigated or, if an application is not approved, until at least 2 years after the investigation is discontinued and regulatory authorities are notified. In addition, ICH 4.9.5 states that the study records should be retained until an amount of time specified by applicable regulatory requirements or for a time specified in the clinical study site agreement between the investigator and sponsor.

Refer to the clinical study site agreement for the sponsor's requirements on record retention. The investigator should contact and receive written approval from the sponsor before disposing of any such documents.

### **6.1.6 Financial Disclosure and Obligations**

The investigator is required to provide financial disclosure information to allow the sponsor to submit the complete and accurate certification or disclosure statements required under 45 CFR 45. In addition, the investigator must provide to the sponsor a commitment to update this information promptly if any relevant changes occur during the course of the investigation and for 1 year after the completion of the study.

Neither the sponsor nor the study clinic is financially responsible for further testing or treatment of any medical condition that may be detected during the screening process.

## **6.2. Confidentiality and Disclosure of Data**

All subjects will sign a HIPAA-compliant authorization form containing the mandated core elements and requirements before participation in this clinical study. The sponsor and designees affirm and uphold the principle of the subject's right to protection against invasion of privacy. Throughout this study, a subject's source data will only be linked to the sponsor's electronic data

capture system database or documentation via a unique identification number. As permitted by all applicable laws and regulations, limited subject attributes such as gender, age or date of birth, and subject initials may be used to verify the subject and accuracy of the subject's unique identification number.

To comply with ICH Guidelines for GCP and to verify compliance with this protocol, the sponsor requires that the investigator allow review of the subject's original medical records (source data or documents) by the study monitor, representatives from any regulatory authority (e.g., FDA), the sponsor's designated auditors, and the appropriate IRB. These medical records will include, but will not be limited to, clinical laboratory test result reports, ECG reports, admission and discharge summaries for hospital admissions occurring during a subject's study participation, and autopsy reports. Access to a subject's original medical records requires the specific authorization of the subject as part of the informed consent process.

Copies of any subject source documents that are provided to the sponsor must have certain personally identifiable information removed (i.e., subject name, address, and other identifier fields not collected in the subject's eCRF).

Data will be maintained and backed up in the electronic data capture system. All access to the data is protected by username and password, and each staff member and all sponsor staff will have separate access that requires a separate username and password. Access is only given to site staff and requested sponsor staff who have completed the appropriate training.

### **6.3. Subject Consent**

Written informed consent in compliance with 45 CFR 46 will be obtained from each subject before entering the study or performing any unusual or nonroutine procedure that involves risk to the subject. An informed consent template may be provided by the sponsor to the study clinic. If any institution-specific modifications to study-related procedures are proposed or made by the study clinic, the consent should be reviewed by the sponsor or its designee or both before IRB submission. Once reviewed, the consent will be submitted by the investigator to the IRB for review and approval before the start of the study. If the informed consent form is revised during the course of the study, all active participating subjects must sign the revised form.

Before enrollment, each prospective subject will be given a full explanation of the study and be allowed to read the approved informed consent form. The informed consent process will be performed by a clinical research nurse in a private room. The subject will be given unlimited time to ask questions regarding study participation, and each subject will be questioned to ensure their understanding. Once the investigator is assured that the subject understands the implications of participating in the study, the subject will be asked to give consent to participate in the study by signing the informed consent form.

The investigator will provide a copy of the signed informed consent form to the subject. The original form will be maintained in the subject's medical records at the site.

## **6.4. Data Collection**

Full details of procedures for data collection and handling will be documented in the data management plan, which is initiated with the final protocol receipt. The data management plan is a changing document that evolves over the course of the study and is finalized by database lock.

## **6.5. Publications**

No information related to or generated by this study will be released to the public until it has been reviewed by the sponsor. The sponsor shall own intellectual rights for the data and analysis resulting from this study. Authorship on publications will be determined by standard journal requirements.

## **7. Study Management**

### **7.1. Monitoring**

The sponsor or its designee will monitor the study to ensure that it is being conducted according to the protocol, GCP standards, and applicable region-specific requirements, and to ensure that study initiation, conduct, and closure are adequate. The investigators and the study clinic staff will be expected to cooperate fully with the study monitors and personnel or agents of the sponsor and be available during monitoring visits to answer questions sufficiently and to provide any missing information. The investigators and their institutions will permit direct access to source data/documents for study-related monitoring activities, audits, IRB reviews, and regulatory inspections.

During any on-site visits, the study monitor will:

- Check and assess the progress of the study
- Review all informed consent forms
- Review study data collected
- Conduct source document verification
- Identify any issues and address their resolution
- Verify that the facility remains acceptable
- Conduct study drug accountability

These monitoring activities will be done in order to verify that the:

- Data are authentic, accurate, and complete.
- The safety and rights of the subjects are being protected.
- The study is being conducted in accordance with the currently approved protocol (including any amendments), GCP, and all applicable regulatory requirements.

In addition, the sponsor, designated auditors, and government inspectors must be allowed access to eCRFs, source documents, and other study files that may be required to evaluate the conduct of the study.

## **7.2. Management of Protocol Amendments and Deviations**

### **7.2.1 Modification of the Protocol**

Any changes in this research activity, except those necessary to remove an apparent immediate hazard to the subject, must be submitted to the sponsor or designee and reviewed and approved by the local IRB before implementation. Amendments to the protocol must be submitted in writing to the investigator's IRB for approval before subjects are enrolled into an amended protocol.

### **7.2.2 Protocol Violations and Deviations**

Any significant protocol deviations that the investigator or study clinic staff believes are of major importance (e.g., incorrect randomizations, subject enrolled but not eligible) should be reported to the sponsor and the investigator's IRB as soon as possible. Significant protocol deviations may include the following:

- Deviations from the inclusion/exclusion criteria that may affect subject safety
- Deviations (omission or delay) of safety monitoring procedures
- Deviations in the administration of the study drug
- Deviations in obtaining informed consent

All subjects who are enrolled and receive the study drug, regardless of whether they have a major protocol violation, must continue to be followed for safety for all follow-up study visits.

8. Appendices

8.1. Appendix A – Schedule of Events

Table 8-1: Schedule of Events

**INDMA in Ranitidine Medicines Clinical Study - Schedule of Events**

	Screening	Check-in/ Baseline	Treatment Period 1								Wash- out	Treatment Period 2														
			1	1	1	1	1	1	1	1		1	1	1	1	1	1	1	1							
Study Day	-28 to -3	-2	1	1	1	1	1	1	1	1	1	1	1	1	1	1	1	1	3	3	3	3	3	3	3	3
Hour			0	0.5	1	1.5	2	3	4	5	6	9	11	12	14	15	24									
Visit	1	2																								
Recruitment/Screening - healthy	X																									
Screening Stipend	X																									
In House Residency		X	X													X										
Meals		X	X	X	X											X										
Informed Consent	X																									
Medical History	X	X																								
Comprehensive Physical exam	X	X																								
Vital Signs	X	X	X																							
Height, Weight	X	X	X																							
12-Lead ECG 	X	X																								
Clinical Chemistry and Hematology 	X	X																								
Urinalysis	X	X																								
SARS-CoV2 Molecular Test		X																								
HIV Test	X																									
Hepatitis Test	X																									
Urine Drug and Alcohol Screen	X	X																								
Pregnancy Test (females only) 	X	X																								
FSH (females only)	X	X																								
H. pylori breath test	X																									
Study agent preparation & application - oral																										
Plasma Sample Collection				X	X	X	X	X	X	X	X	X	X	X	X	X										
Urine Sample Collection 																										
Concomitant Medications		X																								
Adverse Events		X																								

 clinically notable results are repeated  
 serum test  
 Unscheduled urine collections, if any occur, will be collected and processed the same as scheduled urine collections

2.0	General (Rationale)	NDMA analyses will be based on arithmetic means instead of geometric means. Blinded review of the bioanalytical data revealed that a large number of urine and plasma samples for NDMA were below the lower limit of quantification (LLOQ). For multiple subjects, all samples from 1 or more study periods were below the LLOQ. As zero values cannot be log-transformed for geometric mean analyses, these periods would have been removed from analysis. Furthermore, as analyses are paired, these subjects would have been removed from analyses. Utilizing arithmetic mean will allow data from all subjects and all periods to be used in the planned analysis. Ranitidine and DMA analyses will remain the same (i.e. utilizing geometric means).
	7.3.1	Analysis of urine concentrations Analysis of NDMA urine 24-hr excretion will be performed using arithmetic means instead of geometric means.
	7.3.2	Plasma pharmacokinetics Descriptive statistics for plasma PK parameters of NDMA will be calculated using arithmetic means.

1. Introduction

This document outlines the proposed statistical methods for data analysis of data collected from Protocol ‘SCR-010 Clinical study to investigate the urinary excretion of N-nitrosodimethylamine (NDMA) after ranitidine administration’.

2. Objectives

The following analysis plan provides the framework for the summarization of the data from this study. The analysis plan may change due to unforeseen circumstances but will be finalized prior to database lock. Any changes made after the database lock will be documented and justified in the clinical study report.

2.1 Primary Objective

The primary objective is to evaluate 24-hour urinary excretion of N-nitrosodimethylamine (NDMA) after oral administration of ranitidine compared to placebo.

2.2 Exploratory Objectives

Exploratory objectives include the following:

- To evaluate plasma ranitidine, NDMA, and dimethylamine (DMA) after oral administration of ranitidine compared to placebo.
- To evaluate urinary excretion amounts over 24-hours of ranitidine and DMA after oral administration of ranitidine compared to placebo.
- To evaluate 24-hour urinary excretion and plasma concentration of NDMA and DMA with administration of high nitrite/NDMA meals compared to low nitrite/NDMA meals.

3. Study Overview

3.1 Study Design

This is a randomized, placebo-controlled, single-dose, 4-period crossover study with 18 healthy subjects. Subjects will receive 4 treatments over the 4 study periods (see Table 1). Each subject will be randomized to 1 of 4 treatment sequences (i.e., ABCD, ABDC, BACD, or BADC). The treatment will consist of oral administration of either a single dose of ranitidine (300 mg) or placebo administered at time zero on each of 4 different treatment days. All subjects will be provided low nitrite/NDMA meals for the first 2 periods of the study and high nitrite/NDMA meals for the last two periods of the study. Subjects will check in on Day -2 for baseline assessments and will complete each 2-day period over the next 8 days, followed by checkout (see Table 2).

Two different full day menus of low nitrite/NDMA and high nitrite/NDMA meals have been developed. Meals will be identical for treatment periods 1 and 2 (low nitrite/NDMA meals) of the study and a separate set of identical low nitrite/NDMA meals will be served on the washout days prior to treatment. Likewise, meals will be identical for treatment periods 3 and 4 (high nitrite/NDMA meals) and a separate set of identical high nitrite/NDMA meals will be served on the washout days prior to treatment days. The last meal on Day -1, Day 2, Day 4, and Day 6 should be administered at approximately 6 PM to permit at least 12-hour fasting prior to dosing. Subjects will be provided with distilled water to drink throughout the study.

On study treatment days, the first meal will be provided at the time of dosing. Subjects will be instructed to swallow the medication with approximately 250 mL of room temperature distilled water and begin eating within two minutes after dosing. Subjects are required to eat each meal in its entirety during the study. If the meal is not finished, the reason should be recorded, along with what was not eaten, and a picture of the remaining food should be taken.

Urine samples will be collected using separate collection containers over 24 h. Collection times will occur at 0 (pre-dose), 3, 6, 9, 12, 15, and 24 h on study dosing days. Subjects will be instructed to void their bladder at each collection time and total weight of the sample will be recorded. If a subject must void their bladder at an unscheduled time (highly discouraged), the unscheduled voids will be collected, and total weight of the unscheduled voiding will be recorded. The unscheduled voiding sample will be treated, analytically analyzed, and reported as part of scheduled sample collection for determining cumulative amounts of NDMA, ranitidine, and DMA excreted over 24 h. Plasma samples for NDMA, DMA, and ranitidine analysis will be collected at 0 (pre-dose), 0.5, 1, 1.5, 2, 3, 4, 5, 6, 9, 11, 14, and 24 h post-dose on study dosing days.

The study will be conducted at one center in the United States (Spaulding Clinical Research unit in West Bend, Wisconsin). Each treatment group will attempt to include equal representation of male and female subjects.

Table 1: Study Treatments

Treatment	Drug
A	Ranitidine (300 mg) + low nitrite/NDMA meals
B	Placebo + low nitrite/NDMA meals
C	Ranitidine (300 mg) + high nitrite/NDMA meals
D	Placebo + high nitrite/NDMA meals

Table 2: Study Design

Day -2	Day -1	Day 1	Day 2	Day 3	Day 4	Day 5	Day 6	Day 7	Day 8
Check-in	Washout	Period 1	Washout	Period 2	Washout	Period 3	Washout	Period 4	Check-out

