## **4.7. Study Procedures**

### **4.7.1 Pharmacokinetic Assessments**

#### **4.7.1.1 Pharmacokinetic Sample Collection**

Pharmacokinetic blood samples (8 mL for each sample) for determination of ranitidine and NDMA will be collected at the following time points on Days 1, 3, 5, and 7: 0 (pre-dose), 0.5, 1, 1.5, 2, 3, 4, 5, 6, 9, 11, 14, and 24 h.

Blood samples will be collected by direct venipuncture or by inserting an IV catheter into the subject's forearm region. Each blood sample will be labeled with subject number, study number, study day, time point, event, and a barcode that matches that belonging to the subject.

Urine samples will be collected at the following time points on Days 1, 3, 5, and 7 for determination of cumulative amount of ranitidine and NDMA excreted in urine over 24-h: 0 (pre-dose), 3, 6, 9, 12, 15, and 24 h. Subjects will be instructed void their bladder at each collection time and total weight of the sample will be recorded. If a subject must void their bladder at an unscheduled time (highly discouraged), the unscheduled voids will be collected, and total weight of the unscheduled voiding will be recorded. The unscheduled voiding sample will be treated, analytically analyzed, and reported as part of scheduled sample collection for determining cumulative amounts of NDMA, ranitidine, and DMA excreted over 24 h.

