7.3 Pharmacokinetic Analyses

7.3.1 Urine Pharmacokinetics

The primary endpoint is a comparison of 24-h urinary NDMA excretion for ranitidine versus placebo when administered with either low nitrite/NDMA meals (comparison between treatments A and B, respectively) or high nitrite/NDMA meals (comparison between treatments C and D, respectively). No adjustment for multiplicity is planned as these comparisons are considered two separate studies for purposes of our overall design. As an exploratory analysis, 24-h urinary DMA for ranitidine versus placebo will likewise be compared between treatments A and B (low nitrite/NDMA meals) and treatments C and D (high nitrite/NDMA meals). 24-hr urinary excretion of ranitidine (exploratory) will be calculated for treatments A and C, though no

comparisons are planned. Finally, as an exploratory measure, the two placebo-treated treatments (treatment D versus B) will be compared to determine if meals comprised of foods traditionally identified as being higher in nitrites/NDMA result in a higher 24-hr urinary excretion of NDMA or DMA compared to meals identified as being lower in nitrites/NDMA.

The cumulative amount of NDMA (primary), DMA (exploratory), and ranitidine (exploratory) excreted in urine over 24-h for placebo and ranitidine administration will be calculated for each subject. All urine voids over a 24-h period will be collected. Each separate void will be weighed in a tarred container. The volume of the void will be determined assuming a specific gravity of 1.01. Concentration of each collected sample will be used to determine a cumulative amount excreted as follows:

$$Ae_{0-24, \text{compound}} = \sum_{\text{time}} \text{Urine}_{\text{weight, time}} * 1.01 * \text{Conc}_{\text{urine, time}}$$

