Cumulative amounts of DMA and ranitidine will be log-transformed. A mixed-effect analysis of variance (ANOVA) approach will be used for comparing arithmetic means (for NDMA) and geometric means (for DMA and ranitidine) looking at the effects of treatment, period, and sequence. For NDMA, testing will be one-sided at a 0.05 significance level, and a significant increase will be concluded if the lower bound of the one-sided 95% interval for the arithmetic mean difference excludes 0. For DMA and ranitidine, testing will be one-sided at a 0.05 significance level, and a significant increase will be concluded if the lower bound of the one-sided 95% interval for the geometric mean ratio excludes 1. The results will be transformed back to the original scale by exponentiation to provide treatment geometric means.

Normality assumption of the ANOVA will be verified using the Shapiro-Wilke test for normality and homogeneity of variances will be verified using Levene's test. If either assumption is not valid, a Wilcoxon signed-rank test will be used for the comparison rather than an ANOVA.

Individual and mean time course plots of NDMA, DMA, and ranitidine excreted over 24-hr will be evaluated for each treatment. All urine PK parameters will be summarized using descriptive statistics (number of subjects, mean, SD, coefficient of variation [CV], median, minimum, and maximum) for NDMA, DMA, and ranitidine. Individual time course plots will use actual sampling times. Treatment mean plots will use planned sampling times.

All calculations and the hypothesis testing will be done using R software.

Total fraction of the ranitidine dose excreted in urine ($Fe_{0-24, \text{ranitidine}}$) will be determined for Treatments A and C based on the cumulative amount of ranitidine excreted in urine over 24-h ($Ae_{0-24, \text{ranitidine}}$) divided by 300 mg. This will be calculated for each individual, summarized using descriptive statistics (number of subjects, mean, SD, CV, median, minimum, and maximum), and visualized graphically using box-and-whisker plots.

Renal clearance of ranitidine will be determined (only for Treatments A and C) by calculating the rate of excretion as the difference between the later and earlier compound level divided by the difference in times points (i.e., $[\text{amount}_{t_2} - \text{amount}_{t_1}] / [t_2 - t_1]$). The log-transform of the renal

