7.3.2 Plasma Pharmacokinetics

The following PK parameters will be determined for NDMA, DMA, and ranitidine (only Treatments A and C) for each subject based on all available concentration-time points:

- **AUC from time 0 to the sampling time corresponding to the last quantifiable concentration (C_{last}) (AUC_{0-t})**

AUC_{0-t} will be calculated according to the linear trapezoidal rule from 0 h to the last quantifiable concentration after drug administration.

- **AUC from time 0 extrapolated to infinity (AUC_{0-inf})**

AUC_{0-t} will be extrapolated to infinity from the AUC from time 0 to the sampling time corresponding to the last quantifiable concentration plus the last quantifiable concentration divided by K_{el} , as follows:

$$AUC_{0-inf} = AUC_{0-t} + C_{last}/K_{el}$$

- **Maximum concentration (observed peak drug concentration) (C_{max})**

C_{max} will be read directly from the observed concentrations.

- **Time at which C_{max} occurs (T_{max})**

T_{max} will be read directly from the observed concentrations as the blood sampling time corresponding to C_{max} . The earlier time will be reported in cases where the same C_{max} value is observed for a subject at multiple timepoints

- **Terminal half-life ($t_{1/2}$)**

The terminal half-life will then be calculated using the elimination rate constant as:

$$t_{1/2} = \ln(2)/K_{el}$$

- **K_{el}**

The terminal elimination rate constant, which will be determined from the terminal slope of the log-concentration curve using linear regression

The PK parameters will be analyzed using noncompartmental methods based on actual sampling times. Serum concentrations below the limits of quantification will be set to zero for the purpose of this analysis (see Section 6). AUC_{0-inf} , $t_{1/2}$, and K_{el} for each analyte and subject will only be

included if the subject has 3 or more concentration values on the terminal portion of the pharmacokinetic curve and with an adjusted coefficient of determination (R^2) greater than 0.80.

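### Pre-dose DMA is measured in all four periods but left out of the ranitidine-versus-placebo DMA comparisons; using it as a covariate could recover precision at little cost

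*SAP*

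**What the plan says.** SAP 3.1 lists the urine schedule ("Collection times will occur at 0 (pre-dose), 3, 6, 9, 12, 15, and 24 h on study dosing days") and the plasma schedule ("Plasma samples for NDMA, DMA, and ranitidine analysis will be collected at 0 (pre-dose), 0.5, 1, 1.5, 2, 3, 4, 5, 6, 9", continuing to 24 h). Protocol 4.7.1.1 confirms that the pre-dose samples recur in each period: "Urine samples will be collected at the following time points on Days 1, 3, 5, and 7".

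In SAP 7.3.1 the 24-hour amount is a sum over voids with no baseline term ("Concentration of each collected sample will be used to determine a cumulative amount excreted as follows"). The mixed-effect ANOVA is described as "looking at the effects of treatment, period, and sequence". Its fallback is also unadjusted: "If either assumption is not valid, a Wilcoxon signed-rank test will be used for the comparison rather than an ANOVA".

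In SAP 7.3.2 the 0 h plasma value enters only as the first point of the AUC, which is computed "according to the linear trapezoidal rule from 0 h to the last quantifiable concentration after drug administration". AUC0-inf and Cmax are then compared by paired t-test on the original scale, on the log scale if normality fails, and by Wilcoxon signed-rank test if the assumptions still fail.

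The only change-from-baseline summary in either document is for vital signs (Protocol 4.9.8.3, SAP 7.5.3).

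**The concern.** DMA is compared between ranitidine and placebo, and also between the two placebo periods, so the plan expects measurable DMA without the drug. Part of each 24-hour amount or AUC is then background. A value taken just before dosing cannot be altered by that period's dose, and it may predict how much background the subject carries that day.

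Pairing removes stable differences between subjects, and the period term in the urine ANOVA removes shifts common to everyone on a given day. What remains is subject-by-day variation. The part of it that the pre-dose value predicts is left in the error, although the sample is already scheduled. The plasma paired t-test has no period term, so it does not remove common day shifts either. At stake is the width of the intervals for exploratory DMA endpoints.

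**Working it through.** **The plan's own figure.** SAP 3.2 asks for 14 completers, one-sided 0.05, ratio 2, CV 100%, paired comparison on the log scale. Reading the CV as that of the paired difference, SD = √ln(1 + 1²) = 0.833 and the effect is ln 2 = 0.693. The noncentrality is 0.693/0.833 × √14 = 3.12, and with 13 df the power is 90.4%. The stated 14 reproduces and does not rely on any baseline adjustment. It concerns NDMA; the documents give no effect, variance or power for DMA.

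**Effect of the covariate.** Two inputs are assumptions:

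- A comparison that has 80% power without adjustment.
- r, the correlation between the within-subject pre-dose difference and the within-subject outcome difference, varied from 0 to 0.7.

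With 18 subjects and order of treatment within one meal type in the model, error df = 18 − 2 = 16. Power of 80% at one-sided 0.05 then needs a noncentrality of 2.60. Adding one covariate multiplies the variance by (1 − r²)(1 + 1/14) and leaves 15 df. The factor 1 + 1/14 is the average price of estimating the slope. The new noncentrality is 2.60 divided by the square root of that multiplier.

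| r | Variance multiplier | Noncentrality | Power |
|---|---|---|---|
| 0 | 1.071 | 2.51 | 77.3% |
| 0.3 | 0.975 | 2.63 | 80.7% |
| 0.5 | 0.804 | 2.90 | 86.9% |
| 0.7 | 0.546 | 3.52 | 95.6% |

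Power returns to 80% at r of about 0.27. These figures are for a slope fitted within one meal type; a slope common to both is estimated from more data, so the loss at r = 0 is smaller.

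**Covariate or subtraction.** With equal variances, subtracting the pre-dose value multiplies the variance by 2(1 − r), against 1 − r² for ANCOVA before the cost of the slope. At r = 0.3 that is 1.40 against 0.91; at r = 0.5, 1.00 against 0.75. A simulation with 14 subjects and SD 0.833 (about 90% unadjusted) agrees:

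| r | ANCOVA | Change from pre-dose |
|---|---|---|
| 0 | 88% | 68% |
| 0.3 | 90% | 81% |
| 0.5 | 95% | 91% |
| 0.7 | 99% | 98.5% |

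Subtraction loses power below r = 0.5, so the covariate form is the one to use.

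**Which comparisons.** SAP 3.1 has high nitrite/NDMA meals on the washout days before Periods 3 and 4, and low ones before Periods 1 and 2. Within A–B and C–D, both pre-dose samples follow the same washout menu. In D versus B they follow different menus, so the pre-dose value may already carry part of the meal effect under test. Adjusting there could remove some of that effect.

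**The case against.** The strongest reply is that little may be left to explain. Within a meal type the treatment-day menus match, the washout-day menus match, subjects fast for 12 hours before dosing, and pairing plus the urine period term removes most other variation. The size of the remaining subject-by-day variation is not documented. That stands, and it is why r must be shown as a range.

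A reader might take the D versus B comparison as evidence that the plan expects background to vary from day to day within a drug comparison. It is a contrast between meal types and says nothing about two days on the same menu.

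A reader might also infer that the 24-hour background has already been measured. It has not. The pre-dose urine is one void with no stated start of collection, and distilled water is freely available (Protocol 4.8.9), so its concentration partly reflects hydration. It gives a concentration, not a 24-hour amount. Pre-dose plasma DMA is the cleaner covariate.

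Three practical objections also stand. BLQ values are set to zero (SAP 6.1), so their log is undefined. The Wilcoxon fallbacks cannot carry a covariate. The plasma tests start on the original scale. Finally, each pre-dose sample after Period 1 comes 48 hours after the previous dose. If that dose still had an effect, the baseline difference would depend on sequence; the documents show no such carryover.

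**Conclusion.** The pre-dose values are collected in every period and no planned analysis uses them as a baseline. For DMA in A versus B and C versus D this gives up whatever precision they would add. From an assumed 80%, the change in power runs from a loss of about 3 points at r = 0 to a gain of about 16 at r = 0.7, and the gain is under 1 point at r = 0.3. The result rests on an unknown r, an assumed starting power, 18 subjects and no carryover into the pre-dose sample.

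A stronger reading, that the planned drug comparisons are biased or that the primary endpoint is compromised, is not supported. Order of treatment is randomised within each meal type, so leaving out a baseline affects precision only. The primary NDMA endpoint would gain little: the SAP change log reports many samples below the LLOQ, including all samples from whole periods in multiple subjects, and NDMA is now compared on the arithmetic scale. This is an optional improvement to exploratory analyses.

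**What to change.** In SAP 7.3.1 and 7.3.2, before unblinding, prespecify the following for DMA in A versus B and C versus D, and state that it does not apply to D versus B:

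- ANCOVA of the within-subject log DMA difference on the within-subject log pre-dose difference, with period in the model and one slope common to both meal types.
- Pre-dose plasma concentration as covariate for Cmax and AUC; pre-dose urine concentration for Ae0-24.
- Omit the adjusted analysis if pre-dose DMA is BLQ in more than isolated samples, judged on blinded data, and say how an isolated BLQ value is handled.
- Keep the unadjusted Wilcoxon test as fallback if model assumptions fail.
- For NDMA, supportive at most, and omitted if pre-dose values are largely BLQ.

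The same edit should say that the time-0 void is excluded from the Ae0-24 sum, which the formula leaves open.

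No new samples are needed. The cost is one error df and some SAP rewriting. For plasma that is more than one model term, because a log-scale ANCOVA has to replace or sit beside the present t-test sequence.
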